### **Multiple Myeloma (Cohort 2)**

- 1) **Objective:** To evaluate complete response and stringent response rate (CR + sCR) based on IMWG 2006 Criteria in subjects with relapse refractory or refractory MM.
- 2) **Objective:** To evaluate TTP in subjects with relapse refractory or refractory MM.
- 3) **Objective:** To evaluate DOR in subjects with relapse refractory or refractory MM.
- 4) **Objective:** To evaluate PFS in subjects with relapse refractory or refractory MM.
- 5) **Objective:** To evaluate OS in subjects with relapse refractory or refractory MM.
- 6) **Objective:** To compare in bone marrow biopsies, the extent of pre- pembrolizumab PD-L1 expression for pembrolizumab responders versus non-responders in subjects with relapse refractory or refractory MM.

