cPresence/absence of clonal cells is based upon the  $k/\lambda$  ratio. An abnormal  $k/\lambda$  ratio by immunohistochemistry and/or immunofluorescence requires a minimum of 100 plasma cells for analysis. An abnormal ratio reflecting presence of an abnormal clone is  $k/\lambda$  of >4:1 or <1:2.

dRefer to Table 4 for definitions of measurable disease.

**Table 6** International Myeloma Working Group uniform response criteria: disease progression and relapse

Relapse subcategory	Relapse criteria
Progressive disease a To be used for calculation of time to progression and progression-free survival end points for all patients including those in CR (includes primary progressive disease and disease progression on or off therapy)	Progressive Disease: requires any one or more of the following:  Increase of $\geq 25\%$ from baseline in Serum M-component and/or (the absolute increase must be $\geq 0.5 \text{ g/dl}$ ) b Urine M-component and/or (the absolute increase must be $\geq 200 \text{ mg/24 h}$ ) Only in patients without measurable serum and urine M-protein levels: the difference between involved and uninvolved FLC levels. The absolute increase must be $> 10 \text{ mg/dl}$ . Bone marrow plasma cell percentage: the absolute % must be $\geq 10\%$ c Definite development of new bone lesions or soft tissue plasmacytomas or definite increase in the size of existing bone lesions or soft tissue plasmacytomas Development of hypercalcemia (corrected serum calcium $> 11.5 \text{ mg/dl}$ or $2.65 \text{ mmol/l}$ ) that can be attributed solely to the plasma cell proliferative disorder

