Clinical relapse a	Clinical relapse requires one or more of: Direct indicators of increasing disease and/or end organ dysfunction (CRAB features) b It is not used in calculation of time to progression or progression-free survival but is listed here as something that can be reported optionally or for use in clinical practice 1. Development of new soft tissue plasmacytomas or bone lesions 2. Definite increase in the size of existing plasmacytomas or bone lesions. A definite increase is defined as a 50% (and at least 1 cm) increase as measured serially by the sum of the products of the cross-diameters of the measurable lesion 3. Hypercalcemia ( $> 11.5 \text{ mg/dl}$ [ $2.65 \text{ mmol/l}$ ]) (see Table 3 for further details) 4. Decrease in hemoglobin of $\geq 2 \text{ g/dl}$ [ $1.25 \text{ mmol/l}$ ] (see Table 3 for further details) 5. Rise in serum creatinine by $2 \text{ mg/dl}$ or more [ $177 \mu\text{mol/l}$ or more]
Relapse from CR a (To be used only if the end point studied is DFS) d	Any one or more of the following: Reappearance of serum or urine M-protein by immunofixation or electrophoresis Development of $\geq 5\%$ plasma cells in the bone marrow c Appearance of any other sign of progression (i.e., new plasmacytoma, lytic bone lesion, or hypercalcemia see below)

Abbreviations: CR, complete response; DFS, disease-free survival.

aAll relapse categories require two consecutive assessments made at anytime before classification as relapse or disease progression and/or the institution of any new therapy.

bFor progressive disease, serum M-component increases of  $\geq 1 \text{ gm/dl}$  are sufficient to define relapse if starting M-component is  $\geq 5 \text{ g/dl}$ .

cRelapse from CR has the 5% cutoff versus 10% for other categories of relapse.

dFor purposes of calculating time to progression and progression-free survival, CR patients should also be evaluated using criteria listed above for progressive disease.

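### The two calcium limits for myeloma progression, 11.5 mg/dL and 2.65 mmol/L, are not equivalent, so TTP and PFS lack a single hypercalcemia threshold

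*Combined protocol and SAP*

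**What the plan says.** Table 6 in Section 12.7.2 defines progressive disease for Cohort 2. One criterion is enough: "Progressive Disease: requires any one or more of the following". The hypercalcemia criterion reads "Development of hypercalcemia (corrected serum calcium $> 11.5 \text{ mg/dl}$ or $2.65 \text{ mmol/l", and the hypercalcemia must be one "that can be attributed solely to the plasma cell proliferative disorder". A footnote adds a confirmation rule: "All relapse categories require two consecutive assessments made at anytime before classification as relapse or disease progression".

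The table states what this row is for: "To be used for calculation of time to progression and progression-free survival end points for all patients including those in CR". The clinical relapse row below it repeats the calcium pair, this time with the second figure in conversion brackets: "Hypercalcemia ( $> 11.5 \text{ mg/dl}$ [ $2.65 \text{ mmol/l". That row is marked as not used for TTP or PFS.

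Section 3.2 lists the Cohort 2 secondary objectives, among them "To evaluate TTP in subjects with relapse refractory or refractory MM" and "To evaluate DOR in subjects with relapse refractory or refractory MM", as well as PFS. Table 17 in Section 8.2.5.1 analyses all three by Kaplan-Meier summaries, with censoring at the last assessment. The SAP does not write out how DOR is derived.

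The Cohort 2 flow charts (Sections 6.2 and 6.4) place the chemistry panel at local laboratories. Table 13 includes calcium and albumin. No section states a reporting unit, a governing unit for the calcium limit, or a formula for corrected calcium.

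**The concern.** The bracketed form in the clinical relapse row shows that the mmol/L figure is meant as the same limit in another unit, not as a second limit. If the conversion is wrong, the progression row contains two different limits under one name, and the same blood result can be an event or a non-event depending on which figure the reader applies.

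Reading *or* literally does not rescue the wording. The lower limit would then always govern, and the mg/dL figure would never decide anything.

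What is at stake is the event definition for two secondary endpoints in a cohort planned at about 28 subjects. If one subject were reclassified, that would be 1/28 = 3.6% of the cohort.

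**Working it through.** **Inputs.** From Section 12.7.2: 11.5 mg/dL and 2.65 mmol/L. Assumed, because the documents do not give it: molar mass of calcium 40.078 g/mol, checked over 40.0 to 40.1.

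**Formula.** mmol/L = (mg/dL × 10) / molar mass; mg/dL = mmol/L × molar mass / 10.

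**Trying to reproduce the plan's pair.**

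- 11.5 × 10 / 40.078 = 2.869, so 2.87 mmol/L (2.868 to 2.875 over the molar-mass range). The plan says 2.65.
- 2.65 × 40.078 / 10 = 10.62 mg/dL (10.60 to 10.63 over the range). The plan says 11.5.
- Gap: 11.5 − 10.62 = 0.88 mg/dL, or 2.87 − 2.65 = 0.22 mmol/L. In relative terms, 2.869 / 2.65 − 1 = 8.3%.

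**Could anything else explain 2.65?**

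- Rounding of the mg/dL figure: 11.45 to 11.55 mg/dL gives 2.857 to 2.882 mmol/L.
- Rounding of the mmol/L figure: 2.645 to 2.655 mmol/L gives 10.60 to 10.64 mg/dL.
- A different unit: 11.5 mg/dL is 2 × 115 / 40.078 = 5.74 mEq/L.
- A different constant: the pair would need a molar mass of 115 / 2.65 = 43.4 g/mol.

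None of these closes the gap.

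**Control conversions from the clinical relapse row of the same table.**

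- Creatinine, 2 mg/dL, molar mass 113.12 g/mol (assumed): 20 / 113.12 × 1000 = 176.8 µmol/L. The table says 177.
- Hemoglobin, 2 g/dL, monomer mass 16,114 g/mol (assumed): 20 / 16,114 × 1000 = 1.24 mmol/L. The table says 1.25.

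Both reproduce to within rounding. Of the three bracketed conversions, only calcium fails.

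**What is classified differently.** A corrected calcium of 11.0 mg/dL is 11.0 × 10 / 40.078 = 2.74 mmol/L. It exceeds 2.65 mmol/L and does not exceed 11.5 mg/dL. If it is present at two consecutive assessments, is attributed only to the myeloma, and no other progression criterion has been met earlier, the subject has progressed by one figure and not by the other. The same holds for any value above about 10.6 and up to 11.5 mg/dL.

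**What is not affected.** Cohort 2's tested endpoint is ORR. Its rule of at least 12 responses in 28 does not use the calcium limit. Its exact binomial properties (one-sided type I error 0.029 at a 25% rate, power 0.83 at 50%) stand as they are.

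**The case against.** The best case against acting has four parts.

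- *The table is taken from published criteria.* Section 12.7.2 presents it that way, and the documents do not show where the mismatch arose. That stands. But the plan adopts the table as its operating definition, its origin does not make the figures equal, and nothing in the SAP chooses between them.
- *Few subjects can be affected.* Probably so. The criterion asks for hypercalcemia that develops on study, is due to the myeloma alone, and is seen twice; M-protein, light chains, marrow or bone may show progression first. The documents give no calcium distribution, so any count of affected subjects would rest on invented means and variances.
- *The consequence is limited.* TTP and PFS are descriptive, ORR is untouched, and Cohort 2 is closed with everyone off treatment. All true; it limits the weight of the point but does not remove it.
- *Choosing a limit is not a statistical matter.* Correct. Section 5.8 ties stopping of treatment to confirmed progression, and the documents do not show which figure was intended.

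Three stronger readings are tempting, and the documents do not support them.

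- A reader might infer that sites reporting in mmol/L recorded earlier progression than sites reporting in mg/dL. Table 22 in Section 9.1 lists non-US drug supply for the trial as a whole, which makes mixed units plausible. It does not show that any Cohort 2 laboratory reported calcium in mmol/L.
- A reader might infer that DOR is certainly affected. Table 6 names only TTP and PFS, and the SAP gives no DOR derivation.
- A reader might infer that the clinical relapse row adds a second endpoint error. That row is expressly outside TTP and PFS; it matters only as evidence that the pair was meant as a conversion.

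**Conclusion.** The inconsistency is real. The progression row that the plan assigns to TTP and PFS carries two limits 0.88 mg/dL (0.22 mmol/L, about 8%) apart as if they were one, and no section says which governs. The arithmetic needs only the molar mass of calcium, and no plausible value or rounding changes the result.

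The effect is confined to results between about 10.6 and 11.5 mg/dL that also meet the attribution and confirmation conditions, with no earlier progression on another criterion. It reaches TTP and PFS, and reaches DOR on the assumption that response ends at progression. How many subjects fall in that range cannot be derived from the documents; it is probably few. This should be corrected, but it does not threaten the cohort's primary conclusion.

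**What to change.** The sponsor should reconcile the progression and clinical relapse rows of Table 6 by naming one governing calcium limit and giving its true equivalent in the other unit. No view is taken here on which figure is right.

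For the Cohort 2 TTP and PFS analyses:

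1. State how corrected calcium is obtained, and put all values in one unit.
2. Apply the single named limit to every subject, whatever unit the site reported.
3. List every subject whose progression rests only on a corrected calcium between 10.6 and 11.5 mg/dL. Attribution to myeloma remains the site's recorded judgement, since a program cannot decide it.
4. State whether DOR ends at the same progression event; if so, treat it in the same way.
5. Report the change in the CSR. Section 8.1 already allows the Cohort 2 analyses to be modified and the changes reported there.

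The cost is one corrected figure in two rows, a stated correction formula, a unit conversion in the derivation program and a short listing. Calcium and albumin are already collected in the chemistry panel, so no new data are needed.

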### 12.7.3 Lymphoma Disease Response Criteria

Cheson et al. Revised Response Criteria for Malignant Lymphoma. *J Clin Oncol.* 2007; 25:579-586.

Criteria for lymphoma disease assessment:

Table 2. Response Definitions for Clinical Trials				
Response	Definition	Nodal Masses	Spleen, Liver	Bone Marrow
CR	Disappearance of all evidence of disease	(a) FDG-avid or PET positive prior to therapy; mass of any size permitted if PET negative (b) Variably FDG-avid or PET negative; regression to normal size on CT	Not palpable; nodules disappeared	Infiltrate cleared on repeat biopsy; if indeterminate by morphology; immunohistochemistry should be negative
PR	Regression of measurable disease and no new sites	> 50% decrease in SPD of up to 6 largest dominant masses; no increase in size of other nodes (a) FDG-avid or PET positive prior to therapy; one or more PET positive at previously involved site (b) Variably FDG-avid or PET negative; regression on CT	> 50% decrease in SPD of nodules (for single nodule in greatest transverse diameter); no increase in size of liver or spleen	Irrelevant if positive prior to therapy; cell type should be specified
SD	Failure to attain CR/PR or PD	(a) FDG-avid or PET positive prior to therapy; PET positive at prior sites of disease and no new sites on CT or PET (b) Variably FDG-avid or PET negative; no change in size of previous lesions on CT		
Relapsed disease or PD	Any new lesion or increase by > 50% of previously involved sites from nadir	Appearance of a new lesion(s) > 1.5 cm in any axis, > 50% increase in SPD of more than one node, or > 50% increase in longest diameter of a previously identified node > 1 cm in short axis Lesions PET positive if FDG-avid lymphoma or PET positive prior to therapy	> 50% increase from nadir in the SPD of any previous lesions	New or recurrent involvement

Abbreviations: CR, complete remission; FDG, [F]fluorodeoxyglucose; PET, positron emission tomography; CT, computed tomography; PR, partial remission; SPD, sum of the product of the diameters; SD, stable disease; PD, progressive disease.

## 12.8 Interim Analysis Decision Rules

The table below describes the detailed Go/No-Go decision rules for resuming enrollment (GO = Resume enrollment; NG = do not resume enrollment) based on the number of subjects enrolled and number of responses following the interim analysis.

MDS/HL	Number of subjects enrolled at IA			
Number of Responses	10 to 14	15 to 20		
0	NG	NG		
1	NG	NG		
2	GO	NG		
3+	GO	GO		
MM and MLBCL/PD-L1+ NHL	Number of subjects enrolled at IA			
Number of Responses	10 to 11	12 to 15	16 to 18	19 to 20
0 to 3	NG	NG	NG	NG
4	GO	NG	NG	NG
5	GO	GO	NG	NG
6	GO	GO	GO	NG
7	GO	GO	GO	GO

GO = Resume enrollment; NG = do not resume enrollment

## 12.9 Dose Timing Table for Lenalidomide + Pembrolizumab Combination Treatment

Cycle	Weeks	Day	Pembrolizumab 200 mg	Lenalidomide RP2D
Cycle 1	1-4	1	Dose 1	Days 1-21 + 7 days off
		8		
		15		
		22	Dose 2	
Cycle 2	5-8	1		Days 1-21 + 7 days off
		8		
		15	Dose 3	
		22		
Cycle 3	9-12	1		Days 1-21 + 7 days off
		8	Dose 4	
		15		
		22		
Cycle 4	13-16	1	Dose 5	Days 1-21 + 7 days off
		8		
		15		
		22	Dose 6	
Cycle 5	17-20	1		Days 1-21 + 7 days off
		8		
		15	Dose 7	
		22		
Cycle 6	21-24	1		Days 1-21 + 7 days off
		8	Dose 8	
		15		
		22		
Cycle 7	25-28	1	Dose 9	Days 1-21 + 7 days off
		8		
		15		
		22	Dose 10	
Cycle 8	29-32	1		Days 1-21 + 7 days off
		8		
		15	Dose 11	
		22		
Cycle 9	33-36	1		Days 1-21 + 7 days off
		8	Dose 12	
		15		
		22		
Cycle 10	37-40	1	Dose 13	Days 1-21 + 7 days off
		8		
		15		
		22	Dose 14	
Cycle 11	41-44	1		Days 1-21 + 7 days off
		8		
		15	Dose 15	
		22		

Cycle	Weeks	Day	Pembrolizumab 200 mg	Lenalidomide RP2D
Cycle 12	45-48	1		Days 1-21 + 7 days off
		8	Dose 16	
		15		
		22		
Cycle 13	49-52	1	Dose 17	Days 1-21 + 7 days off
		8		
		15		
		22	Dose 18	
Cycle 14	53-56	1		Days 1-21 + 7 days off
		8		
		15	Dose 19	
		22		
Cycle 15	57-60	1		Days 1-21 + 7 days off
		8	Dose 20	
		15		
		22		
Cycle 16	61-64	1	Dose 21	Days 1-22 + 7 days off
		8		
		15	Dose 23	
		22	Dose 22	
Cycle 17	65-68	1		Days 1-21 + 7 days off
		8		
		15	Dose 23	
		22		
Cycle 18	69-72	1		Days 1-21 + 7 days off
		8	Dose 24	
		15		
		22		
Cycle 19	73-76	1	Dose 25	Days 1-21 + 7 days off
		8		
		15		
		22	Dose 26	
Cycle 20	77-80	1		Days 1-21 + 7 days off
		8		
		15	Dose 27	
		22		
Cycle 21	81-84	1		Days 1-21 + 7 days off
		8	Dose 28	
		15		
		22		
Cycle 22	85-88	1	Dose 29	Days 1-21 + 7 days off
		8		
		15		
		22	Dose 30	

Cycle	Weeks	Day	Pembrolizumab 200 mg	Lenalidomide RP2D
Cycle 23	89-92	1		Days 1-21 + 7 days off
		8		
		15	Dose 31	
		22		
Cycle 24	93-96	1		Days 1-21 + 7 days off
		8	Dose 32	
		15		
		22		
Cycle 25	97-100	1	Dose 33	Days 1-21 + 7 days off
		8		
		15		
		22	Dose 34	
Cycle 26	101-104	1		Days 1-21 + 7 days off
		8		
		15	Dose 35	
		22		

## 12.10 Lenalidomide Pregnancy Prevention Plan for Subjects in Clinical Trials

The Pregnancy Prevention Plan (PPP) applies to all subjects receiving lenalidomide within a clinical trial. The following PPP documents are included:

1. The Lenalidomide Risks of Fetal Exposure, Pregnancy Testing Guidelines and Acceptable Birth Control Methods document (Section 12.10.1) provides the following information:
  - Potential risks to the fetus associated with lenalidomide exposure
  - Definition of female of childbearing potential (FCBP)/female not of childbearing potential (FNCPB)
  - Requirements for counseling of all subjects receiving lenalidomide about pregnancy precautions and the potential risks of fetal exposure to lenalidomide
  - Acceptable birth control methods for both female subjects of childbearing potential and male subjects receiving lenalidomide in the study
  - Pregnancy testing requirements for subjects receiving lenalidomide who are FCBP
2. The Lenalidomide Education and Counseling Guidance Document for each gender (female and male; Sections 12.10.6 and Section 12.10.7, respectively) must be completed and signed by a trained counselor at the participating clinical center prior to each dispensing of lenalidomide. A copy of this document must be maintained in the subject's records for each dispense.
3. The Lenalidomide Information Sheet (Section 12.10.8) will be given to each subject receiving lenalidomide. The subject must read this document prior to starting lenalidomide and each time the subject receives a new supply of lenalidomide.

### 12.10.1 Lenalidomide Risks of Fetal Exposure, Pregnancy Testing Guidelines and Acceptable Birth Control Methods

#### 12.10.1.1 Risks Associated with Pregnancy

Lenalidomide is structurally related to thalidomide. Thalidomide is a known human teratogenic active substance that causes severe life-threatening birth defects. An embryofetal development study in animals indicates that lenalidomide produced malformations in the offspring of female monkeys who received the drug during pregnancy. A teratogenic effect of lenalidomide in humans cannot be ruled out. Therefore, a pregnancy prevention program must be followed.

#### 12.10.1.2 Definition of Females of Childbearing Potential

A FCBP is a female who: 1) has achieved menarche at some point, 2) has not undergone a hysterectomy or bilateral oophorectomy or 3) has not been naturally postmenopausal (amenorrhea following cancer therapy does not rule out childbearing potential) for at least

24 consecutive months (ie, has had menses at any time in the preceding 24 consecutive months).

#### **12.10.1.3      Definition of Females Not of Childbearing Potential**

Females who do not meet the above definition of FCBP should be classified as FNCBP.

#### **12.10.2      Counseling**

#### **12.10.2.1      Females of Childbearing Potential**

For a FCBP, lenalidomide is contraindicated unless all of the following are met (ie, all FCBP must be counseled concerning the following risks and requirements prior to the start of lenalidomide):

- She understands the potential teratogenic risk to the unborn child
- She understands the need for effective contraception, without interruption, 28 days before starting lenalidomide, throughout the entire duration of lenalidomide, during dose interruptions and for at least 28 days after the last dose of lenalidomide
- She understands and agrees to inform the Investigator if a change or stop of method of contraception is needed
- She must be capable of complying with effective contraceptive measures
- She is informed and understands the potential consequences of pregnancy and the need to notify her study doctor immediately if there is a risk of pregnancy
- She understands the need to commence lenalidomide as soon as it is dispensed following a negative pregnancy test
- She understands and accepts the need to undergo pregnancy testing based on the frequency outlined in this plan (Section 12.10.4) and in the Informed Consent
- She acknowledges that she understands the hazards lenalidomide can cause to an unborn fetus and the necessary precautions associated with the use of lenalidomide.

The Investigator must ensure that a FCBP:

- Complies with the conditions of the pregnancy prevention plan, including confirmation that she has an adequate level of understanding
- Acknowledges the aforementioned requirements.

#### **12.10.2.2      Females Not of Childbearing Potential**

For a FNCBP, lenalidomide is contraindicated unless all of the following are met (ie, all FNCBP must be counseled concerning the following risks and requirements prior to the start of lenalidomide):

- She acknowledges she understands the hazards lenalidomide can cause to an unborn fetus and the necessary precautions associated with the use of lenalidomide.

### **12.10.2.3 Males**

Traces of lenalidomide have been found in semen. Male subjects taking lenalidomide must meet the following conditions (ie, all males must be counseled concerning the following risks and requirements prior to the start of lenalidomide):

- Understand the potential teratogenic risk if engaged in sexual activity with a pregnant female or a FCBP
- Understand the need for the use of a condom even if he has had a vasectomy, if engaged in sexual activity with a pregnant female or a FCBP
- Understand the potential teratogenic risk if the subject donates semen or sperm.

### **12.10.3 Contraception**

#### **12.10.3.1 Female Subjects of Childbearing Potential**

Females of childbearing potential enrolled in this protocol must agree to use two reliable forms of contraception simultaneously or to practice complete abstinence (True abstinence is acceptable when this is in line with the preferred and usual lifestyle of the subject. Periodic abstinence [eg, calendar, ovulation, symptothermal or post-ovulation methods] and withdrawal are not acceptable methods of contraception.) from heterosexual contact during the following time periods related to this study: 1) for at least 28 days before starting lenalidomide; 2) while taking lenalidomide; 3) during dose interruptions; and 4) for at least 28 days after the last dose of lenalidomide.

The two methods of reliable contraception must include one highly effective method and one additional effective (barrier) method. If the below contraception methods are not appropriate for the FCBP, she must be referred to a qualified provider of contraception methods to determine the medically effective contraception method appropriate to the subject. The following are examples of highly effective and additional effective methods of contraception:

- Examples of highly effective methods:
  - IUD
  - Hormonal (birth control pills, injections, implants, levonorgestrel-releasing intrauterine system [IUS], medroxyprogesterone acetate depot injections, ovulation inhibitory progesterone-only pills [e.g. desogestrel])
  - Tubal ligation
  - Partner's vasectomy
- Examples of additional effective methods:
  - Male condom

- Diaphragm
- Cervical Cap

Implants and levonorgestrel-releasing intrauterine systems are associated with an increased risk of infection at the time of insertion and irregular vaginal bleeding. Prophylactic antibiotics should be considered particularly in subjects with neutropenia.

